The full name of the protein encoded by PDGFRA gene is platelet derived growth factor receptor alpha α . As a cell surface receptor tyrosine kinase, PDGFRA can be activated after binding with its corresponding ligand PDGF, and then activate the phosphorylation pathways of phosphatidylinositol, cAMP and various proteins to regulate cell division and proliferation. Abnormal gene activation may cause tumorigenesis and promote tumor angiogenesis. PDGFRA mutation is closely related to GIST. Currently, up to 85% of patients with GIST have PDGFRA or KIT gene mutations. These mutations are associated with the production of abnormal KIT and PDGFRA proteins, which drive cancer. The two proteins can usually be shut down by imatinib (Glivec) and similar drugs, so as to block the activity of proteins. However, the PDGFRA Exon 18 mutant is very special. It changes the shape of PDGFRA protein, thus preventing the protein from binding to drugs. Meanwhile, clinical studies found that Avapritinib was able to bind to all mutated PDGFRA proteins tested and inhibit their activity in cancer cells. Since the most common mutant of PDGFRA is D842V mutant on Exon 18, the qualitative detection of D842V mutant on PDGFRA

in patients with GIST can be used to assist the concomitant diagnosis of Avapritinib in clinical drug treatment.

Genetron D842V PCR Kit is used for qualitative detection of D842V mutation in Exon 18 of PDGFRA gene in formalin-fixed paraffin-embedded (FFPE) tissue samples of patients with gastrointestinal stromal tumors (GIST), and for concomitant diagnosis of Avapritinib tablets in drug therapy. The result of this kit is for the related sites only, used as a reference for clinicians to choose proper tumor-targeted drugs for patients with GIST, and cannot be used as the only basis for individualized treatment of patients. Clinicians should thoroughly evaluate the detection results based on factors such as patients' condition, drug indications, treatment response and other laboratory indicators.

2 Study Purpose

The primary purpose of this study is to validate and evaluate the safety and effectiveness of Genetron D842V PCR Kit by comparing the results of this kit to those of the simultaneous detection with Sanger sequencing method, calculating the coincidence rate and consistency between the test reagent and the comparison method.

3 Study Design

3.1 Overall Study Design

This trial will be conducted in accordance with the principles of the synchronous blind method. The selected cases will be coded, and the selected samples will be detected with the test reagent and comparison method. When the comparison results are inconsistent with the detection results of Sanger sequencing method, the detection results of sanger will be acceptable. Results will be interpreted independently according to the critical value or interpretation requirements provided by each method, and relevant statistics will be carried out to evaluate the performance of the investigation kits in clinical application.

3.2 Sample Screening

3.2.1 Basis to Determine Sample and Sample Size

$$n = \frac{\left[Z_{1-\alpha/2} \sqrt{P_0(1-P_0)} + Z_{1-\beta} \sqrt{P_T(1-P_T)} \right]^2}{(P_T - P_0)^2}$$

Where, n represents the sample size; $Z_{1-\alpha/2}$ and $Z_{1-\beta}$ are fractions of standard normal distribution, P_0 is the target value of the evaluation indicator, and P_T is the expected value of the evaluation indicator for in vitro diagnostic reagents.

According to the results of preclinical studies, the target value of positive coincidence rate between test reagent and contrast reagent is up to 85% with the expected value up to 99%, the minimum sample size of positive control group is estimated to be 32 cases; if the target value of negative coincidence rate is up to 85% with the expected value up to 90%, the minimum sample size of negative control group is estimated to be 363 cases.

This product is classified as Class III IVD reagent medical device, and the overall sample size of clinical trials should meet the requirements of current relevant laws and regulations. According to the Measures for the *Administration of Registration of In-Vitro Diagnostic Reagents* (CFDA [2014] No. 5) and the *Technical Guidelines for Clinical Trials of In-Vitro Diagnostic Reagents* (CFDA [2014] No. 16), the overall sample size of this clinical trial should not be less than 1,000. It is planned to carry out the trial in at least three clinical sites, with the enrollment of no less than 300 samples at each site. In case of objective reasons, when the sample size is insufficient, appropriate adjustments can be made among the sites to ensure the overall sample size. If the relevant laws and regulations change during the trial, the latest laws and regulations shall prevail, and the number of positive and negative control samples should be statistically significant.

3.2.2 Inclusion, exclusion and elimination criteria

3.2.2.1 Inclusion criteria

- (1) The paraffin-embedded tissue samples of patients clinically diagnosed as gastrointestinal stromal tumors (GIST) are included, and a small number of other cancers or benign lesions in gastrointestinal sites are included as interference samples.
- (2) Samples should have appropriate basic clinical information, including: The patient's unique traceable number, age, sex, pathological diagnosis results, etc.
- (3) The samples are FFPE gastrointestinal stromal tumor tissue samples, and each sample can provide 5 paraffin sections or 5 paraffin rolls with a thickness of at least 5 μm .
- (4) The content of tumor cells meets the requirements of test reagent and comparison method.

3.2.2.2 Exclusion criteria

Those who do not meet any of the above inclusion criteria will be excluded.

3.2.2.3 Elimination criteria

- (1) The investigators consider it inappropriate to continue clinical trials, such as samples prepared without following the required procedures.
- (2) Samples that cannot complete the whole detection process.
- (3) Patients with incomplete sample information.

3.2.3 Sample collection, storage and transportation

Sample collection

The samples will be collected according to the standard pathological operating procedures, the paraffin-embedded pathological section samples should be tested for the content ratio of tumor lesion cells which should meet the requirements of test reagents.

Sample storage and transportation

The FFPE tissue samples within the retention period are transported at normal

temperature, and the extracted nucleic acid is recommended to be detected immediately. Otherwise, DNA should be stored at $-20^{\circ}\text{C}\pm 5^{\circ}\text{C}$ for no more than 6 months, and repeated freezing and thawing should be avoided.

3.2.4 Sample numbering

In principle, only one sample should be collected from one subject, and each subject should have a unique clinical trial number (secondary code). After sample enrollment, before the experimental procedures, the blinding personnel marks the secondary code outside the sample tube, and carefully records the comparison table between the primary code (the unique traceable number of the patient) and the secondary code as the blind codes. Blinding documents shall be kept independently by the blinding personnel until breaking of blindness. Blindness should not be broken under any circumstance during the trial.

During experimental procedures, only the secondary code of samples is reflected.

3.3 Basis to Determine Comparison Method

According to "Technical Guidelines for Clinical Trials of in Vitro Diagnostic Reagents", for newly developed IVD reagents, appropriate subjects will be selected, and the investigational IVD reagents will be simultaneously compared with the "gold standard" for diagnosis in a blinded way in accordance with *Technical Guidelines for Clinical Trials of In-Vitro Diagnostic Reagents*.

For products that have similar products approved for marketing, it is best to use investigational IVD reagents and commercially available products of the same kind as clinical samples for comparative study, so as to demonstrate the equivalency between investigational IVD reagents and commercially available products of the same kind. Based on this principle, for the sites with commercially available products, the commercially available kits will be used for the comparison method; for the sites without commercially available products, Sanger sequencing will be used for the comparison method. There is similar product on the market for the human PDGFRA gene D842V mutation detection kit (PCR-fluorescence probe method), and Sanger sequencing is used as a comparison method.

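### Does the mismatch between the comparator rule in section 3.3 and the choice of Sanger sequencing call for a change to the plan?

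*Protocol*

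**What the plan says.** Section 3.3 of the protocol gives a rule with two branches. The first is: "for the sites with commercially available products, the commercially available kits will be used for the comparison method". The second assigns Sanger sequencing where there is no such product. The rule is then applied to this kit: "There is similar product on the market for the human PDGFRA gene D842V mutation detection kit (PCR-fluorescence probe method), and Sanger sequencing is used" as the comparison method.

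Section 2 describes the purpose of the study as "comparing the results of this kit to those of the simultaneous detection with Sanger sequencing method", and names no other comparator. Section 3.1 describes two methods per sample: "the selected samples will be detected with the test reagent and comparison method". It continues: "When the comparison results are inconsistent with the detection results of Sanger sequencing method, the detection results of sanger will be acceptable". The next sentence of 3.1 begins: "Results will be interpreted independently according to the critical value or interpretation requirements provided by each method".

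Section 4.1 cross-tabulates the test reagent (rows) against the comparison method (columns), with discordant cells B and C. Section 4.2 computes kappa from the same table and takes a value above 0.75 as good consistency.

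**The concern.** The comparator supplies the columns of the fourfold table, and therefore both coincidence rates, both predictive values and kappa. A section written to justify the comparator should not state a premise that leads to a different one. If some centres used a marketed kit and others used Sanger, the pooled table would mix two references.

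The sentence in 3.1 adds to the worry. If Sanger is already the comparator for every sample, the sentence seems to do nothing. If it lets a discordant result be replaced by the Sanger result, reported agreement would partly reflect the replacement and not the kit. It would also seem to sit awkwardly with the independent reading of each method in 3.1 and with the blinding rule in 3.2.4: "Blindness should not be broken under any circumstance during the trial".

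**Working it through.** **Which comparator?** The places that bear on it, side by side:

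| Place | What it points to |
|---|---|
| Section 2 | Sanger |
| 3.1 | one test reagent and one comparison method per sample; Sanger prevails |
| 3.3, rule | kit if marketed, Sanger if not |
| 3.3, market-status clause | a similar product is marketed, hence a kit |
| 3.3, final clause | Sanger |
| 4.2 | kappa against a gold standard |

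Only the market-status clause points away from Sanger. Inserting *no* into it makes 3.3 agree with its own rule and with section 2. The word *sites* in the rule can also mean gene loci: the intended-use paragraph before section 2 says "The result of this kit is for the related sites only", and 4.1 tabulates by locus. The kit covers one mutation, so on that reading the rule gives a single comparator for the whole trial and no mixture across hospitals.

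**What could the 3.1 sentence do to the table?** Kappa = (Pa − Pc)/(1 − Pc), with Pa = (A+D)/N and the standard chance term Pc = [(A+B)(A+C) + (B+D)(C+D)]/N². The protocol gives no counts, so the tables below are assumed, with N = 1,000.

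1. *Sanger is the reference for every sample.* No cell changes. Effect: zero.
2. *Sanger replaces a discordant test-reagent result.* B moves to D and C moves to A, so B = C = 0. Every rate is 100% and kappa is 1.00, whatever the data.
3. *A kit is the comparator, and only the test–kit disagreements are settled by Sanger.* Take A=27, B=97, C=5, D=871. Pa = 0.898 and Pc = (124×32 + 968×876)/1,000² = 0.8519, so kappa = 0.0461/0.1481 = 0.31. If about half of the disagreements are settled for the test reagent, the table is 75/49/3/873. Then Pa = 0.948, Pc = 0.8173 and kappa = 0.72. Agreement rises.
4. *A kit is the comparator, and Sanger replaces the kit result wherever those two differ.* Take A=95, B=10, C=5, D=890. Pa = 0.985, Pc = (105×100 + 900×895)/1,000² = 0.816, kappa = 0.169/0.184 = 0.918. If Sanger reverses five kit results in cell A, the table is 90/15/5/890. Then Pa = 0.980, Pc = (105×95 + 905×895)/1,000² = 0.81995, kappa = 0.16005/0.18005 = 0.889. Positive coincidence goes from 95/100 = 95.0% to 90/95 = 94.7%, and negative coincidence from 890/900 = 98.9% to 890/905 = 98.3%. Agreement falls.

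So the direction is not fixed: readings 2 and 3 raise agreement, and reading 4 can lower it. Readings 3 and 4 need a kit comparator plus Sanger, which is a third result per sample that 3.1 does not describe. Reading 2 would empty cells B and C by construction and leave 4.1 and 4.2 nothing to estimate. Reading 1 is the only one that fits sections 2, 3.1, 4.1 and 4.2 together.

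**Do the plan's own figures depend on this?** No. The formula in 3.2.1 takes only the target and expected rates. With two-sided 0.05 and 80% power (assumed, since the protocol does not give the values), 85% against 99% gives 31.33, hence 32. The pair 85% against 90% gives 362.78, hence 363. Both match the protocol. At these planning values (99% and 90%, with 32 positives and 363 negatives) kappa is 0.59, from Pa = 0.9073 and Pc = 0.7748. That figure reflects the mix of positives and negatives and the planned rates. It does not measure any effect of the comparator.

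**The case for a change.** The strongest case for a change is that the contradiction is certain and on the page. Section 3.3 exists to justify the comparator, it describes comparison with a marketed product as preferable, and it gives no reason for departing from that. A reader cannot tell from the protocol whether a similar product is marketed. The generic mention of contrast reagents in 3.2.1 and section 9 does not help. Choice of comparator is protocol content and is not normally left to the analysis plan. The 3.1 sentence does not say which result yields, or whether the table is built before or after. Correcting both would take two sentences.

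Most of this stands as a comment on drafting: the text is inconsistent and the true market status is unknown. It does not stand as a statistical objection. Whichever way the market-status clause is repaired, the comparator remains Sanger, because sections 2 and 3.3 both say so.

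The two supporting arguments are weak. The independence sentence in 3.1 governs how each assay is read against its own cut-off, and that holds under any reading. The blind codes in 3.2.4 link the patient's traceable number to the sample's secondary code. Two results can be matched by secondary code without opening that link, so the blinding rule neither forbids nor is breached by a comparison of results.

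**Conclusion.** No change to the plan follows. The market-status clause in 3.3 is most likely a clerical slip, and the 3.1 sentence is redundant wording that an analyst will read as naming Sanger the reference. On that reading the same assays are run, the same table is filled, and the coincidence rates and kappa are unaffected: the size is zero.

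This rests on two assumptions, both supported by the text: that Sanger is run as the comparison method on every sample (sections 2, 3.1 and 3.3), and that the fourfold table is filled with each method's own result (the structure of 4.1, which has no replacement step). It would need another look only if a centre in fact used a marketed kit as comparator, or if discordant results were overwritten before tabulation. The protocol describes neither.

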3.4 Study Duration and Reasons for Determination

This clinical study will last about 8 - 12 months from drafting protocol, project establishment, ethical review, agreement signing, specimen collection, detection until the end of experiment, report completion and stamping. If samples are collected smoothly and the sample size meets the trial requirements, the trial duration can be shortened; if it doesn't go smoothly, the duration can be extended appropriately.

4 Statistical Method

4.1 Positive, Negative and Total Coincidence Rates Between Test Reagent and Comparison Method

For each genetic locus, fourfold tables will be used to calculate the positive and negative coincidence rates, positive and negative predictive values, total coincidence rate and their 95% confidence intervals. Using statistical software, Kappa test is used to determine statistical significance of the two detection methods.

Table 1 Result Summary of Clinical Trial Comparing Test Reagent and Comparison Method

Test Reagent	Comparison Method		Total
	Positive	Negative	
Positive	A	B	A+B
Negative	C	D	C+D
Total	A+C	B+D	A+B+C+D

Samples with mutant genotype detected are considered as positive, and samples without mutant genotype are considered as negative.

The calculation formula is:

$$\text{Positive coincidence rate} = A/(A+C) \times 100\%$$

$$\text{Negative compliance rate} = D/(B+D) \times 100\%$$

$$\text{Positive predictive value (PPV)} = A/(A+B) \times 100\%$$

$$\text{Negative predictive value (NPV)} = D/(C+D) \times 100\%$$

$$\text{Total coincidence rate} = (A+D)/(A+B+C+D) \times 100\%$$

The calculation formula of 95% confidence interval: $p \pm 1.96 \times [p(1-p)/n]^{1/2}$ (where P

represents positive and negative coincidence rates, positive and negative predictive values and total coincidence rate, n presents the sample size. If $p > 0.9$, Wilson score method will be used for correction).

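### PPV and NPV in section 4.1 are raw ratios from a table whose share of positives is not tied to D842V frequency in GIST, so they describe the sample rather than GIST patients

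*Protocol*

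**What the plan says.** Protocol section 4.1 states that "fourfold tables will be used to calculate the positive and negative coincidence rates, positive and negative predictive values, total coincidence rate". Each estimate gets a 95% confidence interval. The formulas use raw cell counts: PPV = A/(A+B) and NPV = D/(C+D). They contain no prevalence term, no restriction to GIST samples and no caveat.

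Four other places determine what goes into that table:

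- The background text before section 2 defines the intended use as FFPE tissue from GIST patients, with the result a reference for choosing a targeted drug.
- Section 3.2.1 sizes positives and negatives separately: "the minimum sample size of positive control group is estimated to be 32 cases" and "the minimum sample size of negative control group is estimated to be 363 cases". It then says that "the overall sample size of this clinical trial should not be less than 1,000" on regulatory grounds. It gives no ratio of positives to negatives and no D842V frequency.
- Section 3.2.2.1, criterion (1), adds that "a small number of other cancers or benign lesions in gastrointestinal sites are included as interference samples". Section 4.1 does not take these samples out of the table. (Criterion (3) describes the samples as GIST tissue, which sits awkwardly with criterion (1).)
- Section 7 describes the material as leftover pathology specimens. No section states consecutive or random selection.

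**The concern.** Positive and negative coincidence rates are computed within the columns of the fourfold table, so they do not depend on how many positives and negatives were collected. PPV and NPV are computed within its rows, so they do. A/(A+B) carries over to patients only if the table holds positives and negatives in the proportion found in those patients.

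The protocol prespecifies the row ratios without prespecifying the sampling that would make them interpretable. A reader of the final report could take the PPV as the chance that a kit-positive GIST patient is positive by the comparison method. The figure may instead reflect which archived blocks were available. The interval in section 4.1 is computed conditionally on the mix obtained, so it does not warn of this.

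**Working it through.** **The plan's own figures.** The section 3.2.1 formula gives no numerical alpha or power. I assumed two-sided alpha 0.05 and 80% power because those values reproduce both stated sizes.

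- Positive (target 85%, expected 99%): [1.960 × √(0.85 × 0.15) + 0.8416 × √(0.99 × 0.01)]² / 0.14² = 31.33, rounded up to 32.
- Negative (target 85%, expected 90%): [1.960 × √(0.85 × 0.15) + 0.8416 × √(0.90 × 0.10)]² / 0.05² = 362.78, rounded up to 363.

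Both match. The two sizes therefore come from precision needs in each group, and D842V frequency plays no part in them.

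**Predictive values as a function of the mix.** Write PPA and NPA for the positive and negative coincidence rates and π for the share of positives:

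- PPV = PPA·π / [PPA·π + (1 − NPA)(1 − π)]
- NPV = NPA(1 − π) / [NPA(1 − π) + (1 − PPA)π]

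With the expected values from section 3.2.1 (PPA 0.99, NPA 0.90):

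| Mix (hypothetical) | PPV | NPV |
|---|---|---|
| 32 of 1,000 (π = 0.032) | 0.03168 / (0.03168 + 0.0968) = 24.7% | 99.96% |
| 100 of 1,000 (π = 0.10) | 0.099 / (0.099 + 0.090) = 52.4% | 99.88% |
| 500 of 1,000 (π = 0.50) | 0.495 / (0.495 + 0.050) = 90.8% | 98.9% |
| 637 of 1,000 (negatives at their minimum of 363) | 630.63 / (630.63 + 36.3) = 94.6% | 98.1% |

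Every row meets both stated minima and the total of 1,000. The kit is identical in all of them.

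**Does the section 4.1 interval cover this?** The denominator is the expected number of kit positives.

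- 32 of 1,000: n = 31.68 + 96.8 = 128.5, and 24.7% ± 1.96 × √(0.2466 × 0.7534 / 128.5) gives 17.2% to 32.1%.
- 100 of 1,000: n = 189, giving 45.3% to 59.5%.
- 500 of 1,000: n = 545. Here p exceeds 0.9, so section 4.1 calls for Wilson: centre (0.9083 + 0.0035) / 1.0070 = 0.9054, half-width 0.0243, giving 88.1% to 93.0%.

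These three intervals do not overlap, although kit performance is the same.

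**Interference samples alone.** Assume a D842V prevalence of 5% in GIST and the same NPA in non-GIST tissue. With no interference samples PPV is 34.3%. If 5% of the table is non-GIST, π falls to 0.0475 and PPV to 33.1%. At 10%, π is 0.045 and PPV is 31.8%. At an assumed 10% prevalence the corresponding figures are 52.4%, 51.0% and 49.5%.

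**Sensitivity to NPA.** At 99%/99%, PPV runs from 76.6% (π = 0.032) to 99.0% (π = 0.50). If no false positives are seen (B = 0), the estimated PPV is 100% at any mix.

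**The case against.** The strongest reply is that nothing in the text says the mix is engineered. The sizes 32 and 363 are minima within a larger total and not quotas. The inclusion criteria concern diagnosis, sample information, sections and tumour-cell content, never mutation status. On this reading the share of positives may simply be what archived GIST blocks yield. That stands: a reader might infer enrichment by known mutation status, or that group sizes fix the ratio, and the protocol states neither. It does not state consecutive sampling either, so the condition that A/(A+B) needs is left open.

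A reader might also infer that the interference samples by themselves invalidate PPV. The numbers do not support that: at assumed shares of 5% to 10% they move PPV by about one to three points.

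Nor can the intervals be called misleadingly narrow. At 3.2% and 10% positive they are about ±7 points. What they miss is the dependence on the mix.

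The reply also notes that section 2 rests the trial on coincidence rate and consistency, that PPV and NPV carry no target or acceptance limit, that section 7 says results will not guide care, and that A/(A+B) is a correct description of the table. All of this stands and limits the weight of the point. It does not remove it, because the ratios are reported under names that readers apply to patients.

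Finally, a prevalence-standardised table could be left to an SAP. But section 4.1 already fixes the formula, so an SAP would have to depart from it.

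**Conclusion.** The point holds as a correction to a secondary output. As written, PPV and NPV in section 4.1 do not in general estimate predictive values in GIST patients, because the protocol does not tie the share of positives to D842V frequency in GIST and leaves non-GIST samples in the table.

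The exposure is almost entirely in PPV: 24.7% to 90.8% between 32 positives in 1,000 and a 1:1 mix, at PPA 99% and NPA 90%. NPV changes by about one to two points. The range rests on hypothetical mixes, since the protocol gives no D842V frequency, and on NPA 90%, which is a planning value. It shrinks as NPA rises. If GIST blocks were in fact taken consecutively, the GIST-only ratios could be sound for those sites, but the protocol would have to say so.

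It might be inferred that the trial's main conclusion is at risk. The documents do not support that: the positive and negative coincidence rates do not depend on the mix, and no acceptance rule uses PPV or NPV.

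**What to change.** In section 4.1, derive PPV and NPV from the positive and negative coincidence rates in GIST samples, over a stated range of D842V prevalence π:

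- PPV = PPA·π / [PPA·π + (1 − NPA)(1 − π)]
- NPV = NPA(1 − π) / [NPA(1 − π) + (1 − PPA)π]

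Give an interval at each π that carries the sampling error of both rates. This matters most if B = 0, when the point estimate of PPV is 100% whatever the prevalence. Keep A/(A+B) and D/(C+D) only as descriptive ratios, labelled as specific to this sample, with interference samples excluded.

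The cost is a few lines of text and one small table, with no new samples or tests. The sponsor must state and justify the prevalence range, and PPV may look less favourable at its low end.
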